9.4 Informed consent

Patients undergoing percutaneous or hybrid endovascular intervention for CLTI of the lower limbs will be approached. Before being enrolled on the trial, the participant's written informed consent must be obtained using the CLARITY Consent Form, which follows the PIS. The patient should be given sufficient time after the initial invitation to participate before being asked to sign the Consent Form.

Patients should be given as much time as they require after being given the trial PIS to consider and discuss participation in the trial with friends and family (including their personal legal representative - a person who, by virtue of their relationship, is suitable to act as their legal representative and is available and willing to act, see section 9.4.1). A contact number for someone at the site should be given to the patient should they wish to discuss any aspect of the trial. Following this, the investigator should determine that the patient is fully informed of the trial and their participation, in accordance with the principles of GCP. Patients should always be asked to sign a consent form. One copy should be given to the participant but the original copy should be kept in the ISF and a further copy should be kept with the participant's hospital notes.

Capacity will be assessed by a suitably qualified person at the site before informed consent is received. Informed consent must be obtained prior to the participant being given any medication specifically for the purposes of the trial. Please note, only when written informed consent has been obtained from the patient and they have been registered into the trial can they be considered a trial participant.

The patient's consent to participate in the trial should be taken by those delegated to do so (usually the PI or a medically qualified member of staff who has been delegated this role on the CLARITY delegation log) after a full explanation has been given of the treatment options, including the conventional and generally accepted methods of treatment. All patients must be informed of the aims of the trial, the possible adverse events, the procedures and the possible hazards to which they may be exposed. They will be informed of the strict confidentiality of their patient data, but that their medical records may be reviewed for trial purposes by authorised individuals other than their treating physician.

Participants' consent will be requested to collect: NHS number and postcode to utilise NHS data for future research, and they will be asked to consent to data-linked longer-term follow-up.

Patients participating in the trial may also opt to consent to participate in qualitative interviews (see Section 12.3). This is optional. If trial participants provide their written consent on the CLARITY consent form to indicate their interest in participating in an interview, the local site Research Nurse should go through the separate information sheet with them describing the full details of the qualitative study.

Patients who are eligible for trial participation but decline to participate may opt to consent to participate in qualitative interviews. Patients excluded from trial participation due to polyvascular disease may consent to participate in the qualitative SWAT (see Sections 9.3 and 17). Health professionals involved in the CLARITY trial may consent to participate in qualitative interviews.

Potential interview participants will be identified by the local site PI or Research Nurse, who will provide them with a PIS with details of the qualitative study. Once they have had time to consider the study information, potential interview participants will be asked by the local site PI or Research Nurse to complete a consent to contact form and consent form, which will be securely electronically transferred from the site to the research team. The qualitative researcher may then contact them directly to arrange a suitable time for an interview. If a completed consent form is not received, consent will be taken over the telephone/ videocall and recorded prior to the start of the interview.

Sites are required to send consent forms to the CLARITY Trial Team at the CTR by secure file transfer or encrypted email within 24 hours (or the next working day) of consent being taken. Patient consent will be obtained for this. In instances where the original copy of the consent form cannot be obtained straight away, for example, due to restrictions on paperwork leaving the bed space because of confirmed or suspected COVID-19, the consent form may be sent to the research delivery staff later when able to leave the bed space.

At all follow-up points, research staff will confirm that the patient is happy (continued consent) and still has capacity for ongoing trial participation. The right of the participant to refuse to participate in the trial without giving reasons must be respected. After the participant has entered the trial, the investigator must remain free to give alternative treatment to that specified in the protocol, at any stage, if they feel it to be in the best interest of the participant. However, the reason for doing so should be recorded and the participant will remain within the trial for follow-up and data analysis according to the treatment option to which they have been allocated. Similarly, the participant must remain free to withdraw at any time from the protocol treatment without giving reasons and without prejudicing their further treatment (see Section 10 for further details).

9.4.1 Loss of Capacity during the trial

The site PI, or suitably qualified medical practitioner who has been delegated the role, will confirm suspected loss of capacity.

In the event that a participant gives informed consent and subsequently loses capacity, the participant's initial consent to participate in the trial, given while capable, remains legally valid according to the Medicines for Human Use (Clinical Trials) Regulations, 2004. The participant will remain in the trial unless it becomes apparent that continued participation is not in the best interests of the participant (for medical or other reasons) or if there is any indication that the participant would object to continued participation (based on previous known wishes or any expression of distress or objection), as outlined in the Mental Capacity Act, 2005. Information about options after loss of capacity will be discussed at the time of consent and included in the PIS and consent form.

In cases where a participant's loss of capacity is anticipated to be very short-term or fluctuating, non-safety related activities directly involving the participant (e.g., patient-reported questionnaires) can be temporarily paused. Collection of safety data and clinical data from medical notes may continue When capacity is regained, the participant's willingness to continue in the trial should be confirmed when appropriate (at the next follow up timepoint if not earlier).

If the participant's loss of capacity is anticipated to be for an extended period or capacity is unlikely to be regained (e.g., lost capacity because of dementia), the participant should be withdrawn from the patient-reported questionnaires, and collection of safety data and clinical data from medical notes may continue. If their personal legal representative declines, the participant should be fully withdrawn from the trial. However, if there is a possibility of capacity being regained, the participant should remain in the trial and contacted at the next follow up timepoint.

A participant's personal legal representative should be asked to give informed consent representing the participant's presumed will to continue participating in the trial if:

- There are major protocol changes during the trial
- Or additional consent is required from participants during the trial.

Any request made by a personal legal representative to withdraw a participant from the trial, even if outside of the above conditions, should be considered. If the participant themselves raises any objections, their withdrawal will be processed. An Information Sheet and Consent Form for Legal Representative will be provided.

If the participant does not consent to consulting their legal representative upon losing capacity, or it is not possible to contact their personal legal representative, the participant should be fully withdrawn if the protocol is changed or additional consent is required from participants.

9.5 Registration and randomisation

9.5.1 Registration

Eligible participants with CLTI undergoing percutaneous or hybrid endovascular intervention who have consented to take part in the trial will be registered in the trial before or within 10 days after the procedure. Registration before the procedure will be encouraged. Key information will be collected, including past medical, surgical and drug history. The database will generate a unique trial number which will be the primary identifier for all participants in the trial.

9.5.2 Randomisation

Participants will be randomised within 10 days of the endovascular procedure being performed.

Randomisation will be in a 1:1:1 ratio to receive: (1) clopidogrel alone, (2) aspirin plus clopidogrel or (3) aspirin plus low-dose rivaroxaban for up to 36 months. To reduce the risk of imbalance of key covariates, covariate-adaptive randomisation with a random element will be used for the target artery, antiplatelet loading at the time of procedure and trial site (see Section 14.1). If one arm is dropped due to futility after the interim analysis (see Section 15.1.1), the randomisation ratio will be adjusted to 1:1 between the two remaining arms. This will be detailed in the randomisation plan.

Computerised web-based remote randomisation (available 24 hours a day) will be used. The Trial Manager will also be notified that a participant has been randomised via an automated e-mail alert mechanism to the CLARITY email inbox.

In the event the online randomisation system is unavailable at site or the site has problems accessing the online website, then the local investigator may contact the CTR (during office hours). Randomisation may be performed by CTR staff on request of the local investigator.

If the online system does not work, a telephone back-up managed by the CTR Trial team will be available for use during office hours Monday to Friday:

For online randomisation: A randomisation form must be completed on the trial database to randomise the participant.

For telephone randomisation: A randomisation form must be completed before telephoning the randomisation line.

10 Withdrawal & lost to follow-up

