14.7 Inclusion in analysis

All randomised participants with non-zero follow-up time will be included in the primary intention-to-treat analysis. As part of sensitivity analyses, ineligible participants will be excluded from the analysis, and alternative analysis populations (as described in Section 15.1) will be used.

15 Analysis

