15.1 Main analysis

The final analysis will be performed after the end of the trial follow-up period, which is 48 months after the start of recruitment. Baseline demographic and clinical characteristics will be summarised descriptively by arm.

The primary analysis will be an intention to treat (ITT), including all randomised participants with non-zero follow-up time.

For the composite primary outcome (time from randomisation to the first occurrence of any element of the composite), a two-level Cox proportional hazards regression model will be fitted to estimate hazard ratios, including fixed effects for allocation and random effects to model heterogeneity between sites. Participants are censored at the end of the planned follow-up period (36 months), at

the end of the trial follow-up period, or (in case of dropout) at the time of their last follow-up, whichever occurs first. Regression analysis results will be presented as point estimates with confidence intervals and p-values from a log-rank test, and Kaplan-Meier curves of cumulative event rates at 36 months (31,32) will be generated to compare arms over time.

Primary estimand

Primary outcome question: In patients following endovascular intervention for CLTI, what is the event-free survival time of the three commonly used antithrombotic regimens (clopidogrel; aspirin plus clopidogrel; aspirin plus low-dose rivaroxaban), for those with a non-zero follow-up time?

The primary estimand is described by the following attributes:

- Population: Adults who are first time in CLARITY trial undergoing percutaneous or hybrid endovascular intervention for CLTI of the lower limbs, with atherosclerosis as the cause of CLTI, and with non-zero follow-up time.
- **Endpoint**: The clinical effectiveness endpoint is a composite event-free survival time examined over the trial duration. These events included acute limb ischaemia, major lower limb amputation, myocardial infarction, ischaemic stroke, and all-cause mortality. Participants are censored at the end of the planned follow-up period (36 months), at the end of the trial follow-up period, or (in case of dropout) at the time of their last follow-up, whichever occurs first.
- **Treatment condition**: Clopidogrel, aspirin plus clopidogrel, and aspirin plus low-dose rivaroxaban, regardless of discontinuation or initiation of the antithrombotic regimens.

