15.1.1 Sub-group & interim analysis

A planned interim analysis of the co-primary outcomes will be conducted when 60% of the planned maximum number of primary outcome events have been observed. The interim analysis will compare each of the combination arms against the clopidogrel-only arm (which has the lowest predicted clinical effectiveness) using futility-stopping criteria based on conditional or predictive power which leads to minimal overall power loss. These criteria will be finalised during the trial set-up phase and fully specified in the SAP.

If the futility of the clopidogrel-only arm is shown in at least one of the two comparisons, the trial will continue with the two combination arms only. Participants in the futile arm will continue with the allocated drug and will be followed up until the end of the trial. If all three arms continue through to the final analysis, each of the combination arms will be compared to clopidogrel only, each at 2.5% alpha. If only one is significantly better, it will be declared the most effective. If both combination therapy arms are significantly better, they will then be compared against each other using the full 5% alpha, thus ensuring strong control of the familywise type I error rate.

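### If clopidogrel is closed and allocation becomes 1:1, the stated all-randomised model has no stage term, so any hazard ratio against clopidogrel rests partly on non-concurrent controls

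*Protocol*

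**What the plan says.** **Allocation.** Protocol 9.5.2 starts with three equal arms ("Randomisation will be in a 1:1:1 ratio to receive" one of the three regimens). If an arm is dropped, "the randomisation ratio will be adjusted to 1:1 between the two remaining arms"; 14.1 repeats this.

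**Which arm closes.** Section 15.1.1: "If the futility of the clopidogrel-only arm is shown in at least one of the two comparisons, the trial will continue with the two combination" regimens. One comparison is enough. Those already on clopidogrel stay in: "Participants in the futile arm will continue with the allocated drug and will be followed up until the end of the trial".

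**Analysis set and model.** Section 14.7: "All randomised participants with non-zero follow-up time will be included in the primary intention-to-treat analysis". Section 15.1 repeats the rule ("The primary analysis will be an intention to treat (ITT), including all randomised participants with non-zero follow-up time") and specifies a Cox model "including fixed effects for allocation and random effects to model heterogeneity between sites". Neither section gives a term for stage or calendar period, or restricts comparisons to concurrently randomised participants. The estimand lists all three regimens and makes no exception for a closed arm. The primary safety analysis uses the same model in the on-treatment population.

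**Planned tests.** Section 15.1.1: "If all three arms continue through to the final analysis, each of the combination arms will be compared to clopidogrel only, each at 2.5% alpha". The protocol does not say which contrasts are made if clopidogrel has closed.

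**The concern.** After closure, every clopidogrel participant is an early recruit, while part of each combination arm was randomised when clopidogrel was no longer available. Randomisation protects a comparison only among people who could have been allocated to either arm. If the later recruits differ in underlying risk, a model with allocation and site alone attributes that difference to the drug.

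The clopidogrel estimates can still matter after closure. Futility in one comparison is sufficient, so the other combination's position against clopidogrel may be unresolved, and the pooled model is the only stated route to that hazard ratio and its Kaplan-Meier curves. Bleeding hazard ratios from the same model share the weakness.

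**Working it through.** **Inputs (14.3, 15.1 and 15.1.1).** 12-month event-free survival is 65.0% on clopidogrel, so the hazard is −ln 0.65 = 0.431 per year. HR is 0.65, loss 8% per year, accrual 25/35/40% over three years, N = 3 × 413 = 1,239. The interim is at 60% of planned events and follow-up ends at month 48.

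**Plan's own figure.** With exponential survival and dropout and events counted to month 36, expected events are 157.0 on clopidogrel and about 114 in each combination arm. That is about 385, against the stated 157 + 115 + 115 = 387, so the model reproduces the plan.

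**Interim date.** 0.60 × 387 = 232 events.

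| True HRs of the two combinations | Month of 232 events | Recruited | Still to recruit |
|---|---|---|---|
| 0.65 and 0.65 | 27.7 | 898 | 341 |
| 0.65 and 1.00 | 26.2 | 834 | 405 |
| 1.00 and 1.00 | 24.8 | 778 | 461 |

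**Share of a combination arm without a concurrent control** (first row):
- Immediate closure, total kept at 1,239: 341/2 = 171 late and 898/3 = 299 early, so 171/470 = 36%.
- Immediate closure, combination arms stopped at 413: (413 − 299)/413 = 28%.
- Three-month decision lag (month 30.7), total kept at 1,239: recruited fraction 0.60 + 0.40 × 6.7/12 = 0.823, or 1,020 people; 219/2 = 110 late and 340 early, so 110/450 = 24%.
- Lag and cap together: (413 − 340)/413 = 18%.

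If the combinations are less effective the share is larger. In the second row, with immediate closure and N = 1,239, it is 202.5/(202.5 + 278) = 42%.

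**Effect of drift.** Let d be the baseline hazard of late recruits relative to early ones (assumed; the protocol gives no figure), θ the true HR, and E1 and E2 a combination arm's expected events at month 48 among early and late recruits. The ratio of event rates approximates the Cox HR:

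pooled HR = θ × (E1 + E2) / (E1 + E2/d)

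| Closure month | θ | d | E1 | E2 | Pooled HR |
|---|---|---|---|---|---|
| 27.7 | 1.00 | 0.8 | 181 | 60 | 241/(181 + 75.0) = 0.94 |
| 27.7 | 1.00 | 1.25 | 181 | 84 | 265/(181 + 67.2) = 1.07 |
| 27.7 | 0.65 | 0.8 | 138 | 42 | 0.65 × 180/(138 + 52.5) = 0.61 |
| 27.7 | 0.65 | 1.25 | 138 | 61 | 0.65 × 199/(138 + 48.8) = 0.69 |
| 26.2 | 1.00 | 0.8 | 171 | 73 | 244/(171 + 91.3) = 0.93 |
| 26.2 | 1.00 | 1.25 | 171 | 102 | 273/(171 + 81.6) = 1.08 |

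The last two rows are an internally coherent case: one combination works and triggers closure, and the other is truly no better than clopidogrel. With the three-month lag after month 27.7, the range for θ = 1.00 narrows to 0.96–1.04. With d = 1 there is no bias.

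**Combination against combination.** Both arms have equal allocation in each stage, so drift cancels and the ratio is unchanged.

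**Price of the remedy** (closure at month 27.7, 181 clopidogrel events). With θ = 1.00 and no drift, SE(log HR) is √(1/181 + 1/252) = 0.097 pooled and √(1/181 + 1/181) = 0.105 concurrent, 8% larger. At d = 0.8 the pooled value is √(1/181 + 1/241) = 0.098 and the increase is 7%. At HR 0.65 it is √(1/181 + 1/189) = 0.104 against √(1/181 + 1/138) = 0.113, about 9%. Power with 181 + 138 = 319 events at two-sided 2.5% is Φ(0.431 × √319/2 − 2.241) = Φ(1.61), about 94.6%, ignoring conditioning on the interim result.

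**The case against.** **No confirmatory test is affected.** Section 15.1.1 schedules the 2.5% tests against clopidogrel only if all three arms continue. A reader might infer that the trial's type I error is inflated, or that the clopidogrel contrasts remain the primary question after closure. The document supports neither. It commits to no such test in that branch, and an error rate would also have to account for how often the interim rule closes the arm and for the data that triggered closure. This objection stands and limits the point to estimation.

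**The economic analysis is conditional.** Section 15.3 reports increments for the strategies in the final analysis and follows the interim decision. It does not commit to increments against clopidogrel after closure. This also stands.

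**Drift is hypothetical.** No figure is given, and the possible sources are weak. Smaller sites join after a nine-month pilot, well before the interim, and site is both a minimisation factor and a random effect. The 2026 patent expiry and wider rivaroxaban use are not linked to participants' baseline risk. This stands as to size; a site effect does not, however, remove change over time within sites.

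**The interim may come later.** The 387 events correspond to month 36; follow-up to month 48 would give about 573. If 60% were taken of 573 (344 events), the interim would move to about month 33.9 with 86 still to recruit, a share of 43/(43 + 384) = 10%. The problem shrinks but remains. The protocol's stated planned number is 387.

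**The statistical analysis plan may deal with it.** Possibly, but the protocol itself fixes the primary set and model. What 15.1 defers is additional adjusted analysis.

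**Conclusion.** The point holds in a limited form. If clopidogrel closes, the stated analysis set and model would produce hazard ratios and Kaplan-Meier comparisons against clopidogrel that set some combination participants against earlier controls only. With both HRs at 0.65 the share is about 24–36% of each combination arm (18% if a three-month lag and a cap of 413 coincide), and more if the combinations are less effective. For an assumed drift of 0.8 to 1.25, a true HR of 1.00 reads about 0.94 to 1.07 and a true 0.65 about 0.61 to 0.69; without drift there is no bias. These figures rest on the 14.3 assumptions, closure at month 27.7, N kept at 1,239 and analysis at month 48.

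This concerns the estimates reported after closure, for effectiveness and, through the same model, bleeding. The planned three-arm tests and the comparison of the two combinations are not affected.

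**What to change.** Add to 15.1: if the allocation ratio changes, any contrast with clopidogrel (Cox model, log-rank test or Kaplan-Meier comparison, for effectiveness or safety) is stratified by randomisation stage, before or after the change, or limited to participants randomised while clopidogrel was open. The comparison of the two combinations keeps all participants. Apply the same rule to any contrast with clopidogrel in 15.3. State also which contrasts will be reported after closure, and settle this before the interim result is known.

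The cost is a sentence or two and a stage indicator derived from the randomisation date. The statistical price is a standard error about 7–8% larger for the clopidogrel contrasts (nearer 9% at HR 0.65), because late recruits no longer inform them.

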10.1 Withdrawal

Participants have the right to withdraw consent for participation in any aspect of the trial at any time. The participants' care will not be affected at any time as a result of declining to participate or withdrawing from the trial.

If a participant initially consents but subsequently withdraws from the trial, a clear distinction must be made as to what aspect of the trial the participant is withdrawing from, unless it is not appropriate to contact the participant for this information. These aspects could be:

- 1. Withdrawal from randomisation to receive trial medication
- 2. Withdrawal from trial medication
- 3. Withdrawal from using routinely collected clinical data for the trial (no permission for the research team to look in medical notes to collect health and medication information)
- 4. Withdrawal from follow-up questionnaires (no permission to be contacted by a member of the research team to ask questions about health at 2, 6, 12, 24 and 36 months)
- 5. Withdrawal from contacting alternative contact for completing questionnaires (no permission to be contacted by a member of the research team to ask questions about health at 2, 6, 12, 24 and 36 months)
- 6. (If applicable) Withdrawal from the optional qualitative interview (interview about the trial process)
- 7. Withdrawal of use of participant contact data (personal identifying data collected for the purposes of contacting participants).
- 8. Withdrawal from future data linkage
- 9. Withdrawal from contact regarding eligibility for potential future study
- 10. Withdrawal of consent to all of the above

The withdrawal of participant consent shall not affect the trial activities already carried out and the use of data collected prior to participant withdrawal.

If a participant withdraws form the trial, all endpoint data collected up to the point of withdrawal will be retained and used in analysis as per the GDPR guidelines and the PeRSEVERE principle on retaining data (28). Participants will be informed of this before they join the trial as outlined in the PIS.

All data collected prior to participant withdrawal will be kept with the other trial data and archived after the trial analysis (see section 20 for archiving details).

Furthermore, it is important to collect ongoing safety data at the time of withdrawal, especially if the participant withdraws because of a safety event. There is specific guidance on this contained in the Participant Information Sheet, but briefly: if a participant wishes to stop taking part in the trial completely, they may need to be seen one last time for an assessment and tests. If the participant is suffering a serious reaction to the trial treatment when they decide to stop, information about them will continue to be collected for as long as the reaction lasts.

A participant may withdraw or be withdrawn from trial treatment for the following reasons:

- Intolerance to trial medication
- Serious toxicity
- > Withdrawal of consent for treatment by the participant
- Any alteration in the participant's condition which justifies the discontinuation of the treatment in the Investigator's opinion
- Non-compliance

Participants who consent and subsequently withdraw may complete a withdrawal of consent form if they withdraw in person. However this is not mandatory if deemed not appropriate or burdensome to the participant. In all instances, the withdrawal CRF should be completed on the participant's behalf by the researcher/clinician based on information provided by the participant. This withdrawal CRF should be sent to the CLARITY TM. Any queries relating to the potential withdrawal of a participant should be forwarded to the CLARITY TM.

